Pain: The Modified PEG is adapted from the PEG Pain Scale³⁷ (5 mins), which is used to measure pain over time. Two questions have been added to the initial assessment to measure pain at time of interview and withdrawal related pain. Since many of the infections expected in the study sample are painful, and pain is a driver of opioid use, the PEG will be explored as a secondary outcome measure, moderator and mediator.

HIV Risk: [name] HIV Risk Behavior tool created for NIDA STTR will be used to assess sexual risk behaviors and sharing of IDU related equipment.

Criminal Justice Questionnaire (1 min)- this is a set of 3 questions that asks about probation/parole status, etc.

Interpersonal Violence this is a set of 5 questions that asks about current and past relationships to assess history and current experiences with interpersonal violence. This is derived from the existing Partner Violence Screen (PVS)³⁸ and the Women Abuse Screening Tool (WAST).³⁸

Covid-19 Questionnaire This 9-question assessment seeks to assess: 1) testing for covid-19, 2) diagnosis of covid-19, 3) Changes in substance use and 4) Changes in infection self-management by participants due to the covid-19 pandemic.

Safety:

- Ramsay Sedation Scale³⁹ is a clinical assessment that grades a participant's level of sedation from 1 to 6 and is useful in assessing for excessive opioid agonist symptoms with a score of 3 or greater indicating over sedation and information temporary cessation of further opioid agonist treatment.
- Serious Adverse Events: Death (and cause of death), fatal and non-fatal overdoses, and other serious adverse events via the SAFTEE⁴⁰ as commonly defined under the FDA regulations will be recorded in binary format, and summaries of each event recorded in free text. The SAFTEE has been modified to contain the particular expected AEs for LAB, including serious opioid related adverse events such as non-fatal and fatal overdose.

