Secondary outcomes: 1) Days using opioids, and days injecting drugs per 28 days prior to each major assessment point (weeks 4, 8, 12, and 24 post randomization) (longitudinal, continuous); 2) Urine toxicology-confirmed abstinent (urine toxicology negative for illicit opioids, and self-report negative over past 7 (at week 1) or 30 days (weeks 4, 8, 12, 24) (longitudinal, binary); 3) Completion of the prescribed course of antimicrobial therapy (binary), Re-hospitalization for infection by week 12 (binary); 4) Days using other drugs/alcohol per 28 days prior to each assessment (longitudinal, continuous); 5) Urine toxicology positive for non-opioid drugs (longitudinal, binary); 6) Social functioning and quality of life (WHOQOL-Bref) at 12 and 24 weeks after randomization (longitudinal, continuous); 7) Modified PEG Pain Scale at each assessment (Longitudinal, continuous) 8) HIV risk behaviors—days in past 28 days of vaginal or anal sex without a condom at weeks 4, 8, 12, 24 (longitudinal, continuous); 8) Any needle sharing in past 28 days (longitudinal, binary); 9) Treatment satisfaction (via the TSR)¹² at 12 and 24 weeks (longitudinal, continuous); 10) Discharge “against medical advice” (binary); 11) Cure of index infection (binary); 12) HCV cure or link to treatment (binary); 13) HIV Viral suppression (Viral Load < 200 copies), if HIV positive (binary); 14) overall hospitalization by week 12; 15) ED visits by week 12; 16) Serious adverse events (SAFETEE and non-fatal and fatal overdose) (binary).

Additional variables: *Covariates, primary and secondary analyses: Stratification factors:* Site (3 sites: YNHH; Columbia/Penn State Hershey; South Carolina/Greenville) will be included as a fixed effect in all analyses. *Covariates:* In general, the baseline score for each outcome measure (where applicable) will be included as a covariate in outcome analyses. *Moderators:* A range of baseline moderator variables will be explored including 1) Demographic characteristics (gender, age, ethnicity, living situation (domiciled vs homeless); 2) Modified Pain PEG scores at baseline (continuous) 3) Evidence of fentanyl use at admission (urine toxicology, self-report) (binary); 4) Other substance use at baseline (any cannabis, any stimulant, any heavy drinking days; binary); 5) Probable major depression at baseline (binary based on PHQ score); 5) Type of infection (endocarditis/ osteomyelitis/bacteremia/ cellulitis/ etc.). *Mediators:* 1) Social functioning

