15.0 Risks to Subjects

As in all research studies, there are potential risks. We go to great efforts, however, to ensure that risks are minimized. This is particularly true as we intend to conduct this study with a vulnerable population. Moreover, there is an additional risk with this study, particularly since it initially involves research with those with substance use disorders. Within this section, we will first describe the individual risks associated with the interviews, followed by the laboratory testing, and other potential risks. There may be risks that are currently not known or have yet to be experienced by patients taking Sublocade®.

Risks Associated with Opioid Use Disorder: Opioid use disorder is a dangerous disorder associated with impaired functioning, morbidity (including infections of the type that participants in this protocol will be suffering from on admission), and mortality due to opioid overdose. Patients will be protected from opioid use while inpatient, but the risk of relapse is high after discharge from hospital unless the patient is maintained on one of the effective medications (methadone, buprenorphine, or extended-release naltrexone) which protect against relapse and overdose. Participation in the research study may mitigate these risks to the extent that patients in the ID/LAB arm are started and maintained on long-acting injection buprenorphine, and patients in TAU arm started on and successfully referred to ongoing medication treatment. This risk may differ between study arms to the extent that the ID/LAB arm is more successful at stabilizing patients on maintenance medication.

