In accordance with CT, PA and SC state laws, any new HIV and HCV test results must be reported and this will be outlined in each consent form. We have operated routine HIV and HCV testing for study participants for decades and have extensive experience not only complying with state laws for HIV testing, but with post-test counseling and ensuring engagement in HIV care if indicated. All results will be kept confidential.

Risks Associated with Loss of Confidentiality: As with all research, there is a risk that involves potential breaches of confidentiality. We intend to do everything possible to reduce this risk and this is one of the process measures we propose to measure. Participants with substance and alcohol use disorders are a vulnerable population. Thus, our research to date has insured strict confidentiality safeguards.

Potential sites for breaches of confidentiality include during the recruitment process at the hospital, during study interviews, or from data management systems. From our research efforts and provision of clinical care for out-of-treatment drug users, HCV-infected and HIV infected drug users in clinical settings, we have paid careful attention to potential breaches of confidentiality for subjects undergoing interviews. All information is stored in password-protected, encrypted computers with double-password protection for opening specified files. All confidential information (study instruments, laboratory results, etc.) will be recorded with study participant number only and maintained in locked cabinets within offices at each study site; data will only be available to be opened by the Project Coordinator, Data Manager, co-Principal Investigators, and Statistician. Electronic databases will be maintained through password-protected computers and files and maintained at the Columbia Department of Biostatistics.

Risks associated with long-acting injectable buprenorphine (LAB):

Risks of LAB (Sublocade®) include: increased opioid withdrawal symptoms if the medication is initiated too soon after last opioid dose;

Side effects related to subcutaneous injection: pain, inflammation, or (rarely) infection at the injection site. There have been some reports of severe injection-site reactions causing abscess, ulceration, and necrosis, in some cases requiring surgical depot removal, debridement, antibiotic administration;

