Side effects related to opioids: nausea, constipation, sedation, respiratory depression (particularly when combined with alcohol or other sedating drugs). Opioid use disorder could worsen if the Sublocade® does not prove effective or is discontinued by the patient, including functional impairment as well as risk of death from drug overdose.

Risks associated with Treatment as Usual (TAU): The main risks associated with TAU include: opioid withdrawal symptoms during detoxification; worsening of opioid use disorder, including functional impairment as well as risk of death from drug overdose.

Risks associated with drawing blood include momentary discomfort and/or bruising. Infection, excess bleeding, clotting, or fainting is possible, although unlikely.

Risks associated with pregnancy: If a participant becomes pregnant and tests positive for illegal drugs, it is a law that the South Carolina Department of Social Services (DSS) must be notified.

Participants could be ordered to mandatory drug treatment, lose custody of their children, or be jailed. We will mitigate these risks by performing all pregnancy tests before tests for illegal substances, and by making clear in the consent form these reporting requirements. A person who is found to be pregnant will be withdrawn from the study and no further urine toxicology testing or questions regarding drug use will be queried; they will subsequently be referred to care for both pregnancy and addition. There are no such reporting requirements in Pennsylvania and Connecticut.

Psychiatric Risks:

If someone has a potential new psychiatric diagnosis via any of the structured questionnaires, a study doctor will be notified within 48 hours of the assessment. The participant will be linked for an evaluation and care with a clinician from a designated Psychiatric Team at each site. Participants with existing psychiatric diagnoses will continue their treatments as usual.

If someone is actively suicidal (which can be determined by participant self-report, the PHQ suicidality question OR the MINI suicidality section), each site will follow the general protocol below:

1. If the research staff member is uncomfortable and there is a more experienced clinician available, they will request their assistance. If assistance is not available or the client reports imminent intent to harm self or others, the study staff member will:

If the participant is currently hospitalized, a referral will be made to inpatient psychiatry.

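### The single serious-adverse-event outcome gives overdose and death no by-arm comparison of their own, and pooling would dilute an overdose difference

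*Combined protocol and SAP*

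**What the plan says.** - **Outcome.** Section 12.0, Secondary outcomes, ends with "16) Serious adverse events (SAFETEE and non-fatal and fatal overdose) (binary". No other listed outcome is an adverse-event outcome. Infection re-hospitalization, overall hospitalization and ED visits are separate items.
- **Model.** Under the statistical models for secondary outcomes, binary outcomes get a logistic regression on treatment and site, with a baseline score where relevant. Main effects are tested at two-sided 5%.
- **Collection.** The Safety assessments in Section 10.0 name "Death (and cause of death), fatal and non-fatal overdoses, and other serious adverse events via the SAFTEE", and these "will be recorded in binary format, and summaries of each event recorded in free text". The form also covers events expected with the injection: "The SAFTEE has been modified to contain the particular expected AEs for LAB".
- **Risks.** On opioid use disorder and overdose, Section 15.0 says: "This risk may differ between study arms to the extent that the ID/LAB arm is more successful at stabilizing patients on maintenance medication". For the injection it adds: "There have been some reports of severe injection-site reactions causing abscess, ulceration, and necrosis, in some cases requiring surgical depot removal". For usual care it says: "The main risks associated with TAU include: opioid withdrawal symptoms during detoxification; worsening of opioid use disorder", and goes on to overdose death. Worsening disorder and overdose death also appear in the list for the injection.

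**The concern.** The trial compares two routes into medication treatment, and overdose is the harm that such treatment is meant to prevent. If the item is one indicator, a participant who overdoses counts the same as one with any other serious event. A population hospitalized with serious infection can be expected to have many other serious events in both arms. A difference in overdose would then be a small part of a large, mostly shared total. An odds ratio near 1 for that total would say little about overdose or death, although a reader could take it as reassurance on both. The data would distinguish these events, but the stated analysis would not.

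**Working it through.** **Reproducing the plan's own figure.** The only stated power is for the primary outcome: 100 per arm, 40% vs 59.7%, two-sided 5%. The pooled standard error is √(2 × 0.4985 × 0.5015 / 100) = 0.0707 and the unpooled one is √(0.4 × 0.6/100 + 0.597 × 0.403/100) = 0.0693. Then (0.197 − 1.96 × 0.0707) / 0.0693 ≈ 0.84, which gives power 0.80. The odds ratio is (0.597/0.403)/(0.4/0.6) = 2.22. Both agree with the plan. No power is stated for safety.

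**Inputs for the safety illustration.** From the documents: 100 per arm and two-sided 5%. Assumed, because the documents give no rates: overdose 12% TAU vs 4% ID/LAB; other serious events at the same rate *b* in both arms; event types independent.

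**Formula.** Pooled rate = 1 − (1 − overdose)(1 − *b*). The difference between arms is therefore 0.08 × (1 − *b*). Power is by exact enumeration of two binomials with the pooled z-test.

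| Outcome | TAU | ID/LAB | Difference (points) | Power |
|---|---|---|---|---|
| Overdose alone | 12.0% | 4.0% | 8.0 | 57% |
| Pooled, *b* = 10% | 20.8% | 13.6% | 7.2 | 27.5% |
| Pooled, *b* = 20% | 29.6% | 23.2% | 6.4 | 17.5% |
| Pooled, *b* = 30% | 38.4% | 32.8% | 5.6 | 13.0% |

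The difference itself shrinks only moderately. Most of the lost power comes from the added variance of the shared events.

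**Other assumed overdose rates** (normal approximation):

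| Overdose, TAU vs ID/LAB | Alone | Pooled, *b* = 20% | Pooled, *b* = 40% |
|---|---|---|---|
| 10% vs 5% | 0.27 | 0.09 | 0.06 |
| 15% vs 5% | 0.66 | 0.24 | 0.13 |
| 20% vs 8% | 0.69 | 0.31 | 0.17 |

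**Independence.** Let *s* be the share of overdose patients with no other serious event. The pooled difference is 0.08 × *s*, and independence sets *s* = 1 − *b*. If overdose patients are more likely than others to have another serious event, *s* is smaller and the difference shrinks further. In the opposite extreme of no overlap (*s* = 1) with *b* = 20%, the rates are 32% vs 24% and power is still only 0.24.

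**Offset by events specific to the injection.** Let a share *q* of ID/LAB participants also have such a serious event. The ID/LAB rate becomes 1 − 0.96 × (1 − *b*) × (1 − *q*). With *b* = 30%, *q* = 1% leaves 4.9 points of the 5.6, and *q* = 5% leaves 2.2 (power 6%). Complete cancellation needs 0.96 × (1 − *q*) = 0.88, so *q* = 8.3%.

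**What a separate overdose analysis delivers.** At 12% vs 4% the 95% half-width is 1.96 × √(0.12 × 0.88/100 + 0.04 × 0.96/100) = 7.4 points, around a difference of 8. For 80% power, 15% vs 5% needs 141 per arm and 10% vs 5% needs 435.

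**The case against.** **The item may not be one variable.** The first secondary outcome puts opioid-use days and injecting days under a single type tag, and those are plainly two measures. The last item could likewise mean several binary indicators, which the wording on recording in Section 10.0 would fit. This stands in part: the text is ambiguous. But overdose sits inside the parenthesis that explains serious adverse events, so one indicator is the more natural reading. If several were meant, the plan does not say which, and the same edit settles it.

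**A reader might infer that each arm has its own main harms and that these cancel.** The documents do not support that. Withdrawal, worsening disorder and overdose death are listed for both arms. Injection-site reactions are specific to the injection. Opioid side effects are listed only for it, but usual-care participants may also receive medication treatment. Injection-site infection is called rare, severe reactions are mentioned only as reports, and no rate is given. Near-complete cancellation would need injection-specific serious events about as frequent as the overdose reduction. Partial offset is possible; cancellation is not shown.

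**A reader might infer that this is the only safety analysis.** That cannot be claimed. Hospitalization and ED visits are analysed separately, and the data and safety monitoring plan (Section 13.0) is a separate document that is not available here. What can be said is that the analysis plan has no other adverse-event outcome, and that neither hospitalization nor ED visits isolates overdose or death.

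**The rates are assumptions, and overdose alone is underpowered too.** Both are true. The direction of the dilution does not depend on the particular rates, but its size does. The case for splitting rests on clear estimates, not on gaining an adequate test.

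**Conclusion.** The point holds as a gap in specification with a cheap remedy. On its natural reading, the plan compares one pooled serious-event indicator between arms and promises no by-arm comparison of overdose or death. Section 15.0 allows that the overdose-related risk differs between arms; its wording is conditional and is not a forecast. Under the assumed 12% vs 4%, pooling with other serious events at 10% to 30% cuts power from 57% to between 27.5% and 13.0%. This rests on three things: the single-indicator reading, assumed event rates, and similar background rates in the two arms. Independence is not critical, because power stays low even with no overlap. Dilution is the firm part. Offset by injection-specific events is possible but cannot be sized from the documents.

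**What to change.** In Section 12.0, Secondary outcomes, replace the last item by four outcomes:

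- (a) any overdose, fatal or non-fatal;
- (b) death from any cause;
- (c) serious events of the types that Section 15.0 lists for the injection (injection site, sedation or respiratory depression);
- (d) other serious events.

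State that a fatal overdose counts in both (a) and (b). Report each by arm as number and percentage, with the rate difference and 95% confidence interval, using exact or penalised methods where events are few. Keep any serious event as a descriptive total only.

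The cost is a few lines of text and some extra tables. No new data are needed, since Section 10.0 already names these events separately and the form includes those expected with the injection. The downside is wide intervals for rare components and a few more descriptive comparisons. The text should say that these are for estimation and that the trial is not sized to test overdose.

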For people of child-bearing potential, a urine pregnancy test will be done at baseline prior to urine drug testing. If the test is positive, a confirmatory pregnancy test will be ordered. Participants who are pregnant at baseline will be ineligible to participate in the study. People of child-bearing potential, who are currently pregnant or found to be pregnant upon baseline testing, should be told that they are not eligible for the study without providing a reason. The person should be referred to OB/GYN or Maternal Fetal Medicine program for prenatal care. If they contact the study team at a future timepoint and indicate that they are no longer pregnant and are interested in enrolling in the trial then the Pre-Screener may be readministered.

Urine pregnancy tests will also be done at each follow-up visit. If a participant is found to be pregnant at a follow-up visit: if taking methadone, they will be encouraged to remain on methadone treatment; those who are taking buprenorphine/naloxone formulations will be encouraged to change to sublingual buprenorphine products that do not contain naloxone. Participants who become pregnant while taking study Sublocade® will be discontinued from further administration while they are pregnant, referred for obstetrical and addiction care, and the pregnancy will be followed until an outcome is known.

Study staff will reaffirm to participants that they can remain enrolled in the study no matter the outcome of the pregnancy indicating that their MOUD may need to change or be stopped during pregnancy. Study staff will also instruct participants that they may restart the assigned study medication when they are no longer pregnant if the participant is still within the treatment period of the study. If the participant is beyond the 3-month study intervention window and within the 3-month follow period (i.e., between weeks 12 and 24), the study staff will link the participant to services in the community to re-initiate treatment.

If a participant has severe hepatic disease (i.e. severe transaminitis or advanced decompensated cirrhosis, applied per clinician discretion), they will not be included in the study. LFTs will be monitored on participants for whom they have been ordered by the primary or ID consulting team. If anyone found to have a LFT $>5x$ the upper limit of normal, their study doctor will be notified immediately. Since this will also count as an adverse event, we will follow our DSMP protocol.

Assessments:

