14.0 Withdrawal of Subjects (if applicable)

If the study team feels that the participant's condition is worsening, the team may terminate the participant's study treatment and institute a higher level of care, such as residential treatment or expedited initiation of medication for opioid use disorder. This is outlined in further detail in the DSMP.

As part of the informed consent process, participants will be informed that part of participation in the study means that the study team will track participants into the community who lose contact with the study team and miss appointments for research assessments, and what the tracking involves (e.g. contacting family members and other personal contacts that the participant has listed and given permission to be contacted, looking for the participant in the community in places where he/she is known to frequent). Participants will be informed that they can refuse to engage with study staff and/or ask for their study participation to end and tracking efforts will be discontinued. However, it is our experience from other treatment studies employing active tracking of this type that participants are often grateful for the effort to locate them and typically willing to engage/re-engage with the study team.

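### Sections 10.0 and 15.0 give opposite enrolment instructions for a participant found pregnant during follow-up, and the protocol does not say which governs

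*Combined protocol and SAP*

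**What the plan says.** **Section 10.0 (Laboratory Specifics).** Pregnancy at baseline makes a person ineligible. For later visits, "Urine pregnancy tests will also be done at each follow-up visit". A participant who becomes pregnant on study Sublocade has further doses stopped while pregnant, is referred for obstetrical and addiction care, and the pregnancy is followed to its outcome. On enrolment: "Study staff will reaffirm to participants that they can remain enrolled in the study no matter the outcome of the pregnancy". On study drug, participants are told that "they may restart the assigned study medication when they are no longer pregnant", provided the treatment period is still running.

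**Section 15.0 (Risks associated with pregnancy).** This paragraph describes the South Carolina duty to report a pregnant participant who tests positive for illegal drugs, and the possible consequences: mandatory treatment, loss of custody or jail. It then gives the safeguards: "We will mitigate these risks by performing all pregnancy tests before tests for illegal substances", disclosure in the consent form, and "A person who is found to be pregnant will be withdrawn from the study and no further urine toxicology testing", with drug-use questions also ended. It closes: "There are no such reporting requirements in Pennsylvania and Connecticut".

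**Section 14.0 (Withdrawal of Subjects)** covers clinical worsening, where "the team may terminate the participant's study treatment and institute a higher level of care", and exit at the participant's request. It does not mention pregnancy and refers to the DSMP for further detail.

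**The concern.** A site cannot both keep a participant enrolled and withdraw her. The choice has consequences in each direction.

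- **A site that follows Section 15.0** ends follow-up of a randomized participant, although Section 12.0 analyses everyone randomized. It also removes the restart that Section 10.0 offers. If she leaves before week 12, she misses the visit at which Section 4.0 plans to ask for a release to contact her treatment program. Her primary outcome then rests on a prescription monitoring report or medical record, or on Section 12.0's rule that patients lost to follow-up count as not enrolled in treatment.
- **A site that works from Section 10.0 and its visit lists** finds no cross-reference to the stop on toxicology and drug-use questions. It finds the test order stated only for baseline: "a urine pregnancy test will be done at baseline prior to urine drug testing". In South Carolina these are safeguards against legal harm to the participant.

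**Working it through.** **1. Do the two rules cover the same event?**

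| | Section 10.0 | Section 15.0 |
|---|---|---|
| Event | Found pregnant at a follow-up visit | Participant becomes pregnant; person found pregnant |
| Enrolment | Can remain | Withdrawn |
| Study drug | Stopped while pregnant, may restart | Ends with withdrawal |
| Toxicology and drug-use questions | Not mentioned | Stopped |
| Test order | Pregnancy test first, stated for baseline | Pregnancy test first, all tests |
| Site limit | None | None in the withdrawal sentence |

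The direct conflict is the enrolment row, and the restart depends on it. The last three rows are compatible: Section 15.0 adds to Section 10.0 there.

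**2. Do the visit lists carry the safeguards?** The Study Schedule places a urine pregnancy test at weeks 4, 8, 12 and 24. The Section 10.0 follow-up lists include it at weeks 4, 8 and 24. The Week 12 list has urine toxicology but no pregnancy test. A site using that list could run toxicology at the primary timepoint without the test that should come first.

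**3. How many participants?** Inputs from the documents: about 67 per site-region (Section 6.0) and the expected male share of 60% in Pennsylvania, 70% in South Carolina and 70% in Connecticut (Section 5.0).

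- Women: 67 × 0.40 + 67 × 0.30 + 67 × 0.30 = 26.8 + 20.1 + 20.1 = 67.
- Assumptions, not in the documents: 50-100% of child-bearing potential; 2-5% become pregnant over 24 weeks, evenly over time and across arms.
- Overall: 67 × 0.5 × 0.02 = 0.67 to 67 × 1.0 × 0.05 = 3.35.
- South Carolina: 20.1 × 0.5 × 0.02 = 0.20 to 20.1 × 0.05 = 1.0. Chance of at least one: 1 − 0.98^10 = 18% to 1 − 0.95^20 = 64%.
- Arising by week 12 (half): 0.34 to 1.68 overall.
- Detected at week 4 or 8, so withdrawn before the week-12 visit (8/24): 0.22 to 1.12 overall.

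**4. Effect on power.** The plan's figure first: 100 per arm, 40% against 59.7%, two-sided 5%, pooled two-proportion test without continuity correction, gives 80.03%, and the odds ratio is 2.22. Both match Section 12.0.

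For the worst case, take all 1.68 cases by week 12 as withdrawn and scored not enrolled: 1.68/200 = 0.84%. The rates become 40% × 0.9916 = 39.7% and 59.7% × 0.9916 = 59.2%, a difference of 19.5 points. Power is then about 79.3%.

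**The case against.** **Section 15.0 may concern people found pregnant before follow-up.** Pregnancy is an exclusion, and Section 10.0 removes a participant whose baseline assessments reveal one. But the paragraph opens with a participant who becomes pregnant, and it stops further toxicology. The Study Schedule puts the first pregnancy test at screening and the first toxicology test at baseline, so a person excluded at screening has no study toxicology to discontinue. This reading does not fit.

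**It may be a South Carolina rule.** The rationale is South Carolina law, so this is the better reading. It narrows the conflict to one site but leaves it unresolved there, because Section 10.0 exempts no site.

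**The safeguards are already in the protocol.** This stands. A reader might infer that the plan omits the toxicology stop or the follow-up test order. It does not: Section 15.0 states both without a site limit. What remains is a missing cross-reference and the Week 12 omission.

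**The practical effect is slight.** This also stands. A pregnancy found at week 24 is found at the last visit, and one found at week 12 is found at the primary-outcome visit. The restart matters only in the ID/LAB arm, and only if a pregnancy begins and ends within the treatment period.

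**Withdrawal may be a deliberate legal decision, settled elsewhere.** Possible. The DSMP, the operations manual and the consent form could not be consulted. They could settle practice, but the two protocol sections would still disagree.

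**Conclusion.** The contradiction is real and confined to enrolment status, with the restart depending on it. Under the assumed rates it touches about 0 to 3 participants, at most about one in South Carolina, and power stays near 79%. The counts rest on an assumed pregnancy rate and an assumed share of child-bearing potential. The textual conflict rests on neither.

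Two stronger conclusions are tempting, and the documents support neither. One is that the primary analysis is threatened: the worst-case loss is under one percentage point of power. The other is that week-12 status becomes impossible to ascertain: Section 4.0 allows a prescription monitoring report or medical record, so ascertainment is weakened only. The case for acting is retention of randomized participants and protection of participants in South Carolina, where a single case matters.

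**What to change.** 1. In Section 15.0, replace the withdrawal clause with a statement that a participant found pregnant stops study Sublocade while pregnant and remains enrolled for follow-up as in Section 10.0.
2. Keep Section 15.0's stop on urine toxicology and drug-use questions. The sponsor and IRB should decide whether it applies only in South Carolina, since the reporting duty does not exist at the other sites and stopping there loses opioid-use data for Aim 2.
3. State that week-12 medication treatment status is still ascertained for these participants from the treatment program, prescription monitoring report or medical record.
4. In Section 10.0, cross-reference Section 15.0's test order and toxicology stop. Add the urine pregnancy test to the Week 12 list, ahead of toxicology.

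If the sponsor intends withdrawal for legal reasons, Section 10.0 must be changed instead. One rule has to govern, and the one proposed keeps the legal safeguard without losing the participant.

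The cost is one IRB and consent-form amendment. Keeping the stop forgoes some secondary opioid-use data for about 0-1 participants if it applies in South Carolina only, or about 1-3 if every site stops, under the rates assumed above.
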